Janus Kinases (Jak) are tyrosine kinases (Jak1, Jak2, Jak3 and Tyk2) that bind to cell receptor subunits and mediate the intracellular signalling initiated by interferons (IFN), many interleukins, colony stimulating factors, and hormones such as prolactin, erythropoietin and growth hormone. Following receptor ligation, Jak becomes activated and phosphorylates the latent transcription factors known as signal transducers and activators of transcription (STAT). Then STAT, in homo- or heterodimers, translocate into the nucleus and co-/regulate gene transcription. Mutations of Jak or STAT in humans are associated with severe immune dysfunction, revealing the fundamental role of this pathway in the induction and regulation of immune responses¹ (see Figure below).

Tofacitinib (TOFA), a small molecule that inhibits Jak3, Jak1 and to a lesser degree Jak2, has been proven efficacious in rheumatoid arthritis (RA) in phase III trials^{2,3}. Notably, a series of Jak-STAT signalling cytokines, especially type I IFNs, IL-10 and IL-6, as well as the hormone prolactin, have been implicated in the pathogenesis of systemic lupus erythematosus (SLE)^{4,5}. Such immunological abnormalities are thought to be even more pronounced among subjects with SLE onset early in life, i.e. with SLE diagnosis during childhood and adolescence⁶. In this context, targeting the Jak-STAT pathway may be an attractive approach to manage inflammation and auto-immunity in SLE.

The JAK-STAT signaling pathway. The IL-2 family of cytokines, all sharing a common receptor subunit γ -chain (γ c), play a major role in promoting and maintaining T, B and natural killer (NK) cell populations. The IL-2 receptor family cytokines, after binding their receptor, activate the JAK/STAT signaling pathway. At the cytoplasmic side of the receptor, either JAK1 or JAK3 is phosphorylated. Activation of JAKs (~130 kDa) leads to attraction of a specific combination of STATs (70–94 kDa). IL-2, IL-7 and IL-15 are essential for T cell memory homeostasis, proliferation and survival, while IL-2 and IL-15 are important for NK cell development. IL-2 additionally regulates the homeostatic maintenance of Tregs and their function, and stimulates IFN- γ production by T-cells upregulating the cytolytic properties of CD8+ cytotoxic T cells. IL-4 activates STAT6 and T helper 2 (Th2) development. IL-21, by activating STAT1 and STAT3, induces differentiation of B cells into plasma cells and stimulates cytotoxic T cell proliferation. IL-21 also has regulatory effects, inhibits the antigen-presenting function of dendritic cells (DC), and is a pro-apoptotic factor for NK cells and incompletely activated B cells.

To date, belimumab, hydroxychloroquine, chloroquine and quinacrine are approved for adults with *systemic lupus erythematosus (SLE)*. The latter three medications are approved also for cutaneous lupus without the system form of the disease, i.e. SLE.

Despite these medications, chronic skin disease remains a major problem with SLE⁷. Given the severity of the disease, the unmet medical need, and the low number of available subjects in this specific population, it is judged acceptable to assess the safety, tolerability and PK as primary objectives; and efficacy as secondary objectives in an open-label manner. Subjects with *SLE-cutaneous lesions (SLE- CL)* will be treated with stable standard of care background for SLE and TOFA will be added to treat associated active cutaneous lesions with SLE, based on observed improvement of inflammatory rashes in previous trials of TOFA in various populations. Isolated cutaneous lupus erythematosus without SLE in adults is less common than in older adults and will not be studied⁸.

With respect to SLE-CL, there is an ongoing clinical trial of TOFA in systemic SLE (NCT02535689) where adults with systemic SLE are dosed 5 mg BID. Further, there are several studies supporting the efficacy of TOFA in immune mediated alopecia as can occur with SLE-CL^{9,10}. Studies in children with *Juvenile Idiopathic Arthritis (JIA)*¹¹ suggest that TOFA is well tolerated. Overall, patients found the taste of the TOFA oral suspension to be acceptable (see abstract poster presentation 388 from 2016 ACR meeting¹² (see Appendix 1).

2. Study Design

[figure not shown]
A scheme of the study design and flow is shown in the **figure on the next page**.

This 76-week, 3-part Phase 1b/2 study is intended to evaluate the pharmacological properties (pharmacokinetics and pharmacodynamics), safety, tolerability and preliminary effectiveness of TOFA administrated to young adults (18-45 years) with moderately to severely active SLE-CL. Subjects will be studied at Cincinnati Children's Hospital Medical Center (CCHMC) and Metrohealth Medical Center.

- **Part A** (up to week 8) requires stable background medications;
- **Part B** (up to week 24) allows for tapering of *corticosteroids (CS) in the setting of significant clinical improvement of SLE-CL as defined by a decrease in Cutaneous Lupus Erythematosus Disease Area and Severity Index (CLASI) activity score by $\geq 50\%$ from baseline* , and
- **Part C** (until week 76) permits tapering of other background medications in subjects with clinical remission of SLE-CL (CLASI activity score=0). TOFA dosing is kept stable during Part C.

Cohort 1 (n=10, weight $> 40\text{kg}$ and age ≥ 18 years and ≤ 45 years) will undergo intense PK-sampling to determine exposures following TOFA dosed at 5 mg BID. TOFA dose escalation will not be considered for inadequate response of SLE-CL.

Cohort 2 (n=10, weight $> 40\text{kg}$ and age ≥ 18 years and ≤ 45 years) will be treated with the same dose as Cohort 1. No PK sampling will occur for Cohort 2.

All subjects discontinuing the study after TD1 will enter a 10-Week follow-up period (not shown in figure). TOFA – tofacitinib; study visits at trial day 1 (TD1), day 5 of week 1 **for Cohort 1 only**. Subjects will be discontinued for toxicity or lack of response to TOFA at week 8.

3. Trial Periods -Design

It is planned to enroll a total of 20 subjects aged 18 to 45 years with a body weight of > 40 kg with active SLE-CL that is not controlled by current standard of care medications at tolerable dosages.

Cohort 1 will undergo intense PK-evaluations during the **Intense PK Period of Part A**.

As shown in the figure above, subjects move from Part A to Part B to Part C of the study, unless they are discontinued from the study (see rescue clause, Section 6.5).

It is anticipated that almost all subjects will be treated with stable background therapy with an antimalarial (hydroxychloroquine, rarely chloroquine), up to 80% are treated with corticosteroids (CS), and about 50% of the subjects will also be treated with a non-biological DMARD (mostly methotrexate, azathioprine and mycophenolate mofetil) for prior multiorgan involvement with SLE.

Screening period

Duration up to 4 weeks; however, subjects should have the TD1 visit as soon as possible after the eligibility for the study has been confirmed.

In the event that a laboratory result does not meet inclusion/exclusion criteria for the study, the lab work may be repeated once in the four week period prior to the baseline visit to establish eligibility for the study.

If the subject fails screening for the study, they may be re-screened one time after the screen failure with permission from the sponsor. Subject will retain the same subject number as assigned at the initial study visit.

If a patient discontinues before the baseline visit, only the demographic information and inclusion/exclusion criteria with the primary reason for discontinuation should be completed on the eCRF. It is not necessary to complete all the required evaluations at the time of discontinuation unless medically indicated.

Part A (TD1 – week 8)

The primary objective of Part A is to characterize the PK of TOFA at the 5mg dose based on Cohort 1 data. Standard of care (SOC) therapies are kept stable during Part A. All background medications, including CS remain unchanged.

Cohort 1

Intense PK Period: PK sampling will only be done for subjects in Cohort 1. Starting at TD1, subject will be monitored at least weekly. PK sampling will occur pre-dose on Day 5 (approximately 11-13 hours after the second dose on Day 4) and 0.5, 1, 2, 4 and 8 hours post first dose on Day 5.

Cohort 2

Only if ≥ 1 subject of the Cohort 1 patients has shown partial response of SLE-CL to TOFA by week 4, will **Cohort 2** be enrolled.

Cohort 2 subjects will be seen in weekly intervals during Part A.

Cohort 1 and 2 subjects with clinical remission of SLE-CL can enter Part B as early as week 4 post baseline. Subjects who move from Part A to Part B prior to Week 8, will still be evaluated using the same visit schedule as subjects remaining in Part A until week 8.

Part B (week 8* – 24)

The primary objective of Part B is to assess safety and tolerability of TOFA, secondary objectives include effectiveness. Specifically, the PK of TOFA at the 5 mg dose based on Cohort 1 will be characterized.

- If CS are primarily given for SLE-CL, then CS may be decreased for clinically significant improvement as defined by a *Cutaneous Lupus Erythematosus Disease Area and Severity Index (CLASI)* activity score by $\geq 50\%$ from baseline and must be tapered for CLASI activity scores of 0 for > 2 months.

* Roll-over subjects in SLE-CL clinical remission may enter Part B as early as week 4

- If CS are mainly prescribed for other SLE manifestations besides SLE-CL, then CS can be decreased as per the investigator's decision, based on clinically significant findings of improvement.
- If the subject has been discontinued from CS and continues to be in SLE-CL clinical remission (CLASI activity score = 0), then the subject can enter Part C.

Subjects who move from Parts B to Part C prior to Week 24 will still be seen using the same visit schedule as subjects remaining in Part B until week 24.

Part C (week 24[†] – 76)

During Part C all therapies can be altered, per investigator discretion, with the exception of TOFA. The TOFA dose will remain stable throughout the study. Subjects who exit Part A or B early due to SLE-CL improvement will remain in Part C until they have been in the study for a total of 76 weeks.

4. Study description

4.1 Primary Objective(s) & Endpoint(s)

Primary objective

Part A (Cohort 1 only):

- To evaluate the pharmacokinetic (PK) profiles of TOFA in young adults with SLE-CL who are on stable treatment for SLE

Part A (Cohort 1 and Cohort 2):

- To evaluate the safety and tolerability of TOFA in young adults with SLE-CL

Part B and C:

- To evaluate the safety and tolerability of TOFA in young adults with SLE-CL

Primary endpoints

Part A (Cohort 1 only):

- Day 5: AUC_{inf} and C_{max} of tofacitinib

Part B: At Week 24:

- Nature, severity, and frequency of adverse events
- Incidence and severity of laboratory abnormalities

[†] as early as week 8 for subjects with clinical remission of SLE -CL and off CS

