6.4 Total duration

76 weeks (part A through C) or until TOFA is considered no longer needed by the investigator, whichever is first.

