6.5 Rescue clause, treatment failure & subject withdrawal

A subject will be considered a treatment failure and discontinued from the study if he/she experiences one or more of the following:

- Serious adverse event that is possibly related to TOFA;
- Important worsening of renal disease defined as a persistent increase in proteinuria as measured by the protein: creatinine (PC) ratio to values > 2.0 after achieving complete response of lupus nephritis, or doubling of proteinuria with values PC ratio > 3.0 after achieving a partial response of lupus nephritis;
- Need to increase current or initiation of new SLE background therapy due to non-renal SLE manifestations;
- Life-threatening SLE complications as judged by the investigator;
- Need for more than the protocol defined allowable CS rescue therapy as determined by the treating physician;
- No improvement of SLE-CL as measured by the CLASI by week 8;
- Two sequential absolute lymphocyte counts less than $< 0.5 \times 10^9$ or 500 cells/mm³;
- Two sequential hemoglobin values < 8.0 g/dL (80 g/L) or decreases greater than 2 g/dL on treatment;
- Female subjects that become pregnant during the study will discontinue study treatment. They will be continued to be followed in accordance as outlined in section **7.3.10**.

Subject Withdrawal

Subjects may withdraw from the study at any time at their own/their legal guardian's request, or they may be withdrawn at any time at the discretion of the physician investigators for safety, behavioral, or administrative reasons. If a subject does not return for a scheduled visit, every effort should be made to contact the subject. In any circumstance, every effort should be made to document subject outcome, if possible.

The investigator will inquire about the reason for withdrawal, request the subject to return all unused investigational product, request the subject to return for a final visit, if applicable, and follow-up with the subject regarding any unresolved AEs.

7 If the subject withdraws from the study, and also withdraws consent for disclosure of future information, no further evaluations should be performed, and no additional data should be collected. The sponsor may retain and continue to use any data collected before such withdrawal of consent. Planned Assessments & Evaluations

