7.1 Evaluations for ALL Subjects

PART A

Cohort 1: Subject will be monitored at Day 1 and Day 5 of week 1, and then once per week during weeks 2, 3, 4, 5, 6, 7, 8.
PK samples will be drawn on Day 5 of Trial Week 1: pre-morning dose and 0.5, 1, 2, 4 and 8 hours post-morning dose of Day 5.

Cohort 2: TD1, and then once per week during weeks 2, 3, 4, 5, 6, 7, and 8.

PART B[‡]

Subjects of Cohorts 1 and 2 will be monitored at study visits at weeks 10, 12, 16, 20 and 24. CS dosing can be changed during Part B.

PART C[§]

Subjects of Cohorts 1 and 2 will be monitored at study visits every 8 weeks until week 76. Background medications, CS and other background medications can be changed during Part C, while TOFA remains stable.

Follow-up Period

All subjects who discontinue TOFA treatment at any time post-baseline will have a follow up phone call 10 weeks after the last TOFA dose to monitor for the development of safety events.

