7.3.2. Reporting Period

For SAEs, the active reporting period to the IRB and Pfizer begins from the time that the subject provides informed consent, which is obtained prior to the subject's participation in the study, i.e., prior to undergoing any study-related procedure and/or receiving TOFA, through and including 28 calendar days after the last administration of the investigational product.

SAEs occurring to a subject after the active reporting period has ended should be reported to the IRB, FDA, and PFIZER if the investigator becomes aware of them; at a minimum, all serious adverse events that the investigator believes have at least a reasonable possibility of being related to study drug are to be reported to the IRB, FDA and PFIZER.

AEs (serious and non-serious) will be recorded on the CRF from the time the subject has taken at least one dose of study treatment through last subject visit.

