8.2 Safety Analyses

The safety population will be all subjects who received at least 1 dose of TOFA. No interim analyses are planned.

AE, SAEs and serious adverse events will be summarized using frequencies and under consideration of the number of study subjects affected. Further, in secondary analysis, we will use mixed model analysis to assess the relationship between side effects and (1) subject weight (2) background therapy with CS; (3) concurrent use of a nonbiological immunosuppressant, or (4) a history of lupus nephritis.

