See details in Protocol Section 8, Planned Statistical Analyses.

Categorical outcomes parameters will be summarized in frequencies/ rates and numeric outcomes will be assessed using paired t-tests. In analyses that adjust for concomitant medications, ANOVA will be done and least-square means calculated.

Frequencies of adverse events by seriousness will be summarized per MEDDRA lower level term and/or NCI Common Toxicity Criteria lower-level term.

K. REGULATORY ISSUES

ADVERSE EVENT REPORTING DEFINITIONS

Adverse Event (AE)

An AE is any untoward medical occurrence in a clinical investigation subject administered a product or medical device; the event need not necessarily have a causal relationship with the treatment or usage.

Serious Adverse Event (SAE)

An SAE is any untoward medical occurrence at any dose that:

- Results in death;
- Is life-threatening (immediate risk of death);
- Requires inpatient hospitalization or prolongation of existing hospitalization;
- Results in persistent or significant disability/incapacity (substantial disruption of the ability to conduct normal life functions);
- Results in congenital anomaly/birth defect.

Requires or Prolongs Hospitalization: Hospital admissions scheduled prior to the study, are not considered serious adverse events unless the hospitalization is prolonged due to an adverse event. Planned admissions as part of a study, hospitalizations for scheduled treatment of a pre-existing condition that has not worsened, and hospitalization for an elective procedure are not considered serious adverse events.

AE/SAE DATA COLLECTION AND REPORTING

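### No planned adverse event summary allows for unequal exposure time, and the protocol leaves unsettled whether safety is primary and when AE recording ends

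*Combined protocol and SAP*

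**What the plan says.** **Summaries.** Section 8.2 states that AEs and SAEs "will be summarized using frequencies and under consideration of the number of study subjects affected", in everyone who received at least one dose. It adds a secondary mixed model relating side effects to weight, corticosteroid use, other immunosuppressants and nephritis history. Appendix 3 J says: "Frequencies of adverse events by seriousness will be summarized per MEDDRA lower level term". Neither place mentions person-time.

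**Length of follow-up.** Section 2 provides for discontinuation at week 8 for toxicity or lack of response. Section 6.5 lists "No improvement of SLE-CL as measured by the CLASI by week 8" as treatment failure, and also any possibly TOFA-related SAE, which can occur earlier. Section 6.4 sets treatment at 76 weeks "or until TOFA is considered no longer needed by the investigator, whichever is first".

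**End of recording.** Section 7.3.2 records AEs on the CRF from "at least one dose of study treatment through last subject visit". SAEs have an active reporting window of 28 days after the last dose, and beyond that "SAEs occurring to a subject after the active reporting period has ended should be reported" if the investigator learns of them. Section 7.1 plans that subjects who stop TOFA "will have a follow up phone call 10 weeks after the last TOFA dose to monitor for the development of safety events".

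**Status of safety.** Section 4.1 and Appendix 3 B make safety a primary objective in all three parts. Their only primary safety endpoint stands under "Part B: At Week 24".

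**The concern.** Everyone dosed is in the denominator. A subject who leaves at week 8 without an event counts the same as one observed event-free for 76 weeks. A low AE percentage at the end of the study could mean low risk or many early exits, and the planned tables would not separate the two. The study has no control arm, so the subjects' own exposure is the only internal yardstick.

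Two gaps in definition add to this. Sites cannot tell from 7.3.2 whether a non-serious AE first mentioned at the ten-week call goes on the CRF. The standing of the safety data, most of which would accrue after week 24, depends on which section is read.

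**Working it through.** **1. Exposure.** From the documents: N = 20, exit point week 8, primary safety time point week 24, end at week 76. The exit share f is not given; 0, 25% and 50% are assumed, with all exits at exactly week 8 and everyone else treated to week 76.

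- Week 0–8: 20 × 8/52 = 3.1 PY
- Week 8–24: 20(1−f) × 16/52
- Week 24–76: 20(1−f) × 52/52

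| f | 0–8 | 8–24 | 24–76 | Total PY | Share after week 24 |
|---|---|---|---|---|---|
| 0 | 3.1 | 6.2 | 20.0 | 29.2 | 68% |
| 25% | 3.1 | 4.6 | 15.0 | 22.7 | 66% |
| 50% | 3.1 | 3.1 | 10.0 | 16.2 | 62% |

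**2. Crude percentage.** Assume a constant on-treatment rate r, an off-drug rate r_off over the ten weeks after an early exit, and exits unrelated to AE risk. Through week T:

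P = f[1 − exp(−(8r + 10r_off)/52)] + (1−f)[1 − exp(−rT/52)]

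With r = 0.5 per PY, T = 76 and f = 0.5:

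- No exits: 1 − exp(−0.5 × 76/52) = 51.8%.
- r_off = r, call recorded: 0.5 × 15.9% + 0.5 × 51.8% = 33.9%.
- r_off = 0, or call not recorded: 0.5 × 7.4% + 0.5 × 51.8% = 29.6%.

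In each range below, the first figure takes r_off = r with the call recorded, and the second takes r_off = 0 or the call unrecorded.

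| r per PY | T (weeks) | f = 0 | f = 25% | f = 50% |
|---|---|---|---|---|
| 0.5 | 76 | 51.8% | 42.9–40.7% | 33.9–29.6% |
| 1 | 76 | 76.8% | 64.9–61.2% | 53.0–45.5% |
| 0.5 | 24 | 20.6% | 19.4–17.3% | 18.3–14.0% |
| 1 | 24 | 37.0% | 35.0–31.3% | 33.1–25.6% |

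**3. Is one pooled rate enough?** Suppose instead that risk is front-loaded: 3 per PY to week 8, then 0.5 per PY, with no off-drug events. Expected first events to week 8 are 20[1 − exp(−3 × 8/52)] = 7.39 over 7.39/3 = 2.46 PY at risk. After week 8 they are 20(1−f) × exp(−3 × 8/52) × [1 − exp(−0.5 × 68/52)], that is 6.05, 4.54 and 3.03 over 12.10, 9.08 and 6.05 PY.

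| f | Crude | Pooled rate per 100 PY | To week 8 | After week 8 |
|---|---|---|---|---|
| 0 | 67% | 92 | 300 | 50 |
| 25% | 60% | 103 | 300 | 50 |
| 50% | 52% | 122 | 300 | 50 |

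The pooled rate moves with exits although the hazards are unchanged. The two period rates do not move.

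**4. Precision.** At r = 1 with a constant hazard and no off-drug events, expected on-treatment first events to week 76 are 20P = 15.36, 12.23 and 9.11, over as many PY at risk. Rounded to 15, 12 and 9 events, the exact Poisson 95% intervals are 55–161, 51–171 and 45–188 per 100 PY.

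**5. Status of safety, place by place.**

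- Primary: the background text before Section 2; 4.1 (Parts A, B and C); 6.3; Appendix 3 A and B.
- Secondary: the opening of Section 6; Appendix 3 D.
- Section 3: PK as the primary objective of Part A, safety for Part B, none named for Part C.
- Primary safety endpoint: week 24 only, so Parts A and C have a primary safety objective in 4.1 without an endpoint of their own.

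**6. End of recording.** 7.3.2 does not define the last visit. Sections 7.3.12 and 7.3.13 send all reported AEs to the CRF, and Appendix 3 L speaks of follow-up safety visits. These favour recording what the call finds, but no section says that the call counts as a visit. The Section 10 table as extracted ends at week 76/EOS with no follow-up column.

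**The case against.** The case against has force in several places.

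- Section 8.2 is not confined to crude frequencies, because it also plans the mixed model. That is correct, but the model names no exposure term, so the gap remains.
- The large contrast is at week 76. By week 24, with the call recorded and the same off-drug rate, the fall is small: 37% to 33–35% at 1 event per PY. This stands.
- If the off-drug rate really is zero, the lower percentage truthfully reports that fewer subjects had events. This also stands: the crude figure is not false, but it cannot be read as a risk without exposure beside it.
- Exit shares and event rates are assumed, and with no exits there is no effect. Subjects who leave because of an AE already count as affected, so the dilution comes from those who leave without one.
- A pooled rate can depend on exits as well (step 3), and intervals from 20 subjects are wide. Both are accepted and shape the fix.
- No safety test or AE comparison with other studies is planned, so the primary or secondary label changes no planned analysis. True, but the objectives still contradict one another.

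Three stronger readings are tempting and not supported. A reader might infer that late safety events are lost; SAEs are covered by the 28-day window and the awareness rule, and for non-serious AEs the text is ambiguous, not plainly contradictory. A reader might infer that data after week 24 go unanalysed; AEs are scheduled to week 76 and 8.2 has no cut-off. A reader might take 8 to 76 weeks as the range of follow-up; exits can come before week 8.

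**Conclusion.** The point holds in this form. Exposure is unequal by design and no planned AE summary accounts for it. Through week 76 the crude percentage could fall from 52% to 30–34% with no change in the on-treatment rate, under an assumed constant 0.5 events per PY and an assumed 50% leaving at week 8. At week 24 the effect is smaller. The size rests on those assumptions and on exits being unrelated to AE risk. The absence of an exposure-based summary does not rest on them.

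The conflict over the status of safety is a plain inconsistency in the text. About 68% of planned exposure (62% if half leave at week 8) lies beyond the only primary safety time point. The end of AE recording is an undefined term that affects non-serious events first reported at the ten-week call. These are worthwhile corrections to a small descriptive study. They do not show that its safety results would be invalid.

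**What to change.** 1. **Section 8.2 and Appendix 3 J.** Beside the subject counts, report subjects with a first event and total events per 100 PY at risk, separately for TD1 to week 8, weeks 8–24, weeks 24–76 and post-treatment follow-up. Show the number at risk and the PY in each period, with exact Poisson 95% intervals for the first-event rates. Treat intervals for total events as descriptive, since events cluster within subjects. Do not rely on a single pooled week-76 rate.
2. **Section 7.3.2.** State that AE recording on the CRF runs through the ten-week follow-up contact described in 7.1.
3. **Status of safety.** Reconcile the background text, Section 3, 4.1, the opening of Section 6, 6.3 and Appendix 3 A, B and D. If safety is primary for Parts A and C, give them safety endpoints through week 8 and through week 76/EOS. Otherwise take those parts out of the primary safety objective.

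The cost is a few extra tables, CRF entries for events found at a call already planned, and changes of wording. No patients or visits are added. The rates will be imprecise and descriptive only, so they supplement the counts and do not replace them.
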